7.4.6.1.1. Definition and Severity Categorization of Hypoglycemic Events

Based on review of the subject completed hypoglycemia assessment logs at each outpatient visit to the site, the Investigator must assess the glucose values as well as any symptoms documented. Each hypoglycemic event will be reported by the Sponsor according to the following categories.

Severe Hypoglycemia: An event requiring assistance of another person to actively administer carbohydrate, glucagon, or other resuscitative actions. These episodes may be associated with sufficient neuroglycopenia to induce seizure or coma. Finger-stick or plasma glucose measurements may not be available during such an event, but neurological recovery attributable to the restoration of plasma glucose to normal is considered sufficient evidence that the event was induced by a low plasma glucose concentration.

Documented Symptomatic Hypoglycemia: An event during which typical symptoms of hypoglycemia are accompanied by a measured finger-stick or plasma glucose concentration ≤ 70 mg/dL (3.9 mmol/L).

Asymptomatic Hypoglycemia: An event not accompanied by typical symptoms of hypoglycemia but with a measured finger-stick or plasma glucose concentration ≤ 70 mg/dL (3.9 mmol/L).

Probable Symptomatic Hypoglycemia: An event during which symptoms of hypoglycemia are not accompanied by a fingerstick or plasma glucose determination, but was presumably caused by a plasma glucose concentration ≤ 70 mg/dL (3.9 mmol/L). Since many people with diabetes choose to treat symptoms with oral carbohydrate without a test of plasma glucose, it is important to recognize these events as probable hypoglycemia.

7.4.6.1.2. Guidance on Adverse Events Related to Hypoglycemia

All episodes considered as likely to represent symptomatic hypoglycemia by the Investigator must be captured as an adverse event of "symptomatic hypoglycemia." This diagnosis may be supported by, but does not require, confirmatory blood glucose results (such as those measured using a fingerstick or from a clinical laboratory sample). Further, at the discretion of the Investigator, an asymptomatic finger-stick or plasma glucose value ≤ 70 mg/dL (3.9 mmol/L) from either a fingerstick or central laboratory sample may be reported as an adverse event of "asymptomatic hypoglycemia." General guidance regarding the determination as to whether an event is considered to be an adverse event should be followed (see [Section 8.1](#)).

7.4.7. Assessment of Infections

7.4.7.1. Urinary Tract Infections

Any subject presenting with symptoms considered to be a urinary tract infection should be recorded as having an adverse event with the term as considered appropriate by the investigator (eg, cystitis, pyelonephritis, urinary tract infection). The site should collect urine for culture performed by their local laboratory, but urine dipstick should not be performed by the site or local laboratory. If a urinalysis is clinically necessary, a microscopic urinalysis ONLY and not a dipstick urinalysis should be performed. If symptoms are reported outside of a routine scheduled study visit, clinical assessment and urine testing should be done promptly at an unscheduled visit. The investigator or treating physician should initiate antibiotic treatment as considered clinically appropriate; if possible, a locally obtained culture and sensitivity should be obtained. The choice of antibiotic agent and duration of treatment is left to the investigator's or treating physician's discretion.

Additionally, if a subject reports a urinary tract infection treated by another physician, this episode will be captured as an adverse event. The site should attempt to obtain information from the treating physician regarding diagnostic tests performed (excluding urine dipstick results) and treatment provided, and this information should be recorded.

7.4.7.2. Genital Fungal Infections

Subjects who suspect that they have a genital fungal infection should be encouraged to report this to Investigators. The Investigator or treating physician can initiate antifungal treatment either empirically as per local practice or following results from genital swab collected and analyzed by the central laboratory. The choice and duration of antifungal agent used is left to the Investigator or treating physician's discretion.

7.5. Pharmacokinetics of Ertugliflozin

7.5.1. Plasma for PK Analysis

On the morning of any visit that includes pharmacokinetic sampling, investigational product dosing (if applicable) will occur after the pre-dose sample is taken.

Blood samples (approximately 4 mL) to provide approximately 2 mL of plasma for pharmacokinetic analysis will be collected at visits specified in the "[Schedule of Activities](#)". Pre-dose samples will be collected at Weeks 6, 12, 18 and 30. In addition, post-dose samples will be collected at Weeks 12 and 18, 1 hour after administration of investigational product (but with an allowable window up to 3 hours). The exact date and time of the blood draw and the date and time of the last dose of investigational product reported by the subject prior to the blood draw should be captured on the CRF.

Samples will be centrifuged at approximately 1700 g for about 10 minutes at 4°C (if a refrigerated centrifuge is not available, place sample in an ice water bath for at least 10 minutes before centrifugation). The plasma will be stored in appropriately labeled screw-capped polypropylene tubes at approximately -20°C within 1 hour of collection.

Detailed instructions for the preparation and shipment of the samples can be found in the Laboratory Manual supplied by the central laboratory.

As part of understanding the pharmacokinetics of the investigational product, samples may be used for metabolite identification and/or evaluation of the bioanalytical method. These data will be used for internal (ie, Sponsor) exploratory purposes and will not be included in the clinical study report.

7.6. Dual-Energy X-Ray Absorptiometry (DXA)

7.6.1. Bone Mineral Densitometry

Bone densitometry will be performed in facilities qualified and approved by the Sponsor or its designee.

DXA scanning procedures will be standardized and all the scans will be monitored and centrally analyzed by a Central Evaluation Facility according to a specific protocol. Procedures to be followed by the bone densitometry facilities to maintain quality control will be provided in a separate manual. The hardware used should remain the same for the duration of the trial. Software upgrades to DXA equipment must be approved in advance by the Central Evaluation Facility.

BMD of lumbar spine (L₁-L₄), femoral neck, and total hip and distal forearm will be measured by DXA at all time-points as mentioned in the [Schedule of Activities](#). The left hip should be evaluated unless prevented by pathology, in which case the right hip will be evaluated throughout the trial.

Screening DXA scan should be performed at Screening Visit 3, or sometime between S3 and at least ten days before the Day 1 visit. These scans will be submitted to the Central

Evaluation Facility for assessment of eligibility. Assessment of eligibility will be returned to the site before Day 1 visit and results of the Screening DXA must be available prior to subject randomization.

Follow up DXA scans will be performed at Week 26, 52 and 104 visits and submitted to the Central Evaluation Facility for assessment. Follow-up scans should be obtained in a ± 14 day window from the scheduled Week 26, 52 visits and in a 14 day window prior to the Week 104 visit. Investigators will remain blinded to the results of these follow up scans, unless the subject meets criteria for rescue criteria as provided below.

In case of discontinuation of investigational product during Phase A, a DXA scan will be performed if the discontinuation occurs between Week 12 and Week 26. In case of discontinuation of investigational product during Phase B, a DXA scan will be performed if the discontinuation occurs at least 12 weeks from the previous scan.

7.6.1.1. Rescue Criteria Related to Loss of BMD

Rescue criteria will be put into place for subjects who exhibit a significant reduction in BMD according to the protocol-defined criteria. Subjects with a reduction in BMD from baseline of $>7\%$ at any anatomical site together with a T-score <-2.5 at the Week 26 or Week 52 follow-up scans, will have a complete unscheduled DXA performed. If these values are confirmed based on a repeat, complete unscheduled DXA the Investigator or treating physician will be permitted to start any bone active therapy. In these cases, subjects should continue to receive ertugliflozin or matching placebo. The repeat, confirmatory DXA should be performed within 4 weeks from the initial reading.

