6.2.3. Placebo Run-in (Visit S3 or Combined S2/S3)

A separate S3 visit is required for subjects taking metformin monotherapy for less than 8 weeks at the S1 visit and for those who require a change to their diabetes regimen (including subjects who need to discontinue their AHA therapy). Subjects whose HbA1c at S1 is 7.0-10.5% (53-91 mmol/mol), and are on metformin monotherapy ≥ 1500 mg/day for 8 weeks or more at S1 can proceed with a **combined S2/S3 Visit**. If visit is combined S2/S3, all procedures from each individual visit must be performed at the one combined visit.

Subjects will return to the site after a minimum **10-hour fast** (except water) for S3 or combined S2/S3. The following procedures should be completed:

- Update concomitant medications since last visit.
- Measure HbA1c to assess eligibility for subjects taking metformin monotherapy for less than 8 weeks at the S1 visit and for those who required a change to their diabetes regimen at the S2 visit (including subjects who have discontinued their AHA therapy at the S2 visit).
- Conduct inquiry about any spontaneously reported adverse events by asking the subjects to respond to a non-leading question such as “how do you feel?”
- DXA of lumbar spine, total hip, femoral neck and distal forearm [refer to [Section 7.6](#)]. DXA should be performed on the same day as the S3 visit. However, if it cannot be performed on this day, the DXA will need to be conducted sometime between S3 and at least ten days before the Day 1 visit in order that the results will be available prior to Day 1.
- Perform complete physical examination [refer to [Section 7.3](#)].

- Obtain duplicate orthostatic blood pressure and pulse rate measurement (supine → standing) [refer to [Section 7.4.3](#)].
- Measure body weight in duplicate [refer to [Section 7.2](#)].
- Obtain blood sample for 25-hydroxyvitamin D measurement.
- Urine pregnancy test for women of childbearing potential.
- Perform a fasting finger stick blood glucose assessment at the clinic.
- Diet and exercise monitoring (see [Section 6.1.2](#)).
- Review self-monitoring blood glucose and Hypoglycemia Assessments logs completed by the subjects (refer to [Section 7.4.6](#)).
- Review of eligibility criteria.

Following completion of the above procedures:

- Contact IVRS.
- Provide subject with glucose meter supplies and additional self-monitoring blood glucose or hypoglycemia assessment logs, as needed.

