6.4.4. Week 104 (Visit 15) – Final Study Visit/Early Termination Visit

At Week 104 \pm 14 days relative to Day 1 (V4) or at Early Termination (ET), subjects will return to the site after a minimum **10-hour fast** (except water).

Completion of the Week 104 (V15) visit marks the end of the subject's participation in Phase B. Subjects who complete the trial and those who discontinue from the trial prematurely, should complete the procedures listed below:

- Contact IVRS.
- Update concomitant medications since last visit.
- Assess treatment compliance with investigational product and blinded glimepiride/placebo therapy (if applicable).
- Measure body weight in duplicate [refer to [Section 7.2](#)].
- Collect triplicate measurements of sitting blood pressure and pulse rate [refer to [Section 7.4.2](#)].
- Obtain supine, single, standard, 12-lead ECG [refer to [Section 7.4.4](#)].
- DXA of lumbar spine, total hip, femoral neck and distal forearm [refer to [Section 7.6](#)]. If the DXA can't be performed at Week 104 visit, it can be obtained in a 7 days window prior to Week 104. In case of discontinuation of investigational product during Phase A, a DXA scan will be performed if the discontinuation occurs between Week 12 and Week 26. In case of discontinuation of investigational product during Phase B, a DXA scan will be performed if the discontinuation occurs at least 12 weeks from the previous scan.
- Conduct brief physical examination which includes assessment of heart, lungs, abdomen, extremities and skin.
- Conduct inquiry about any spontaneously reported AEs by asking the subjects to respond to a non-leading question such as "how do you feel?" Assess potential clinical events for adjudication [refer to [Section 7.8](#)].
- Review self-monitoring blood glucose and Hypoglycemia Assessment Logs completed by the subject [refer to [Section 7.4.6](#)].
- Perform a fasting finger stick blood glucose assessment at the clinic.
- Diet and exercise monitoring (see [Section 6.1.2](#)).
- Obtain blood **and** urine specimens for:

090177e1848ce2dd\Approved\Approved On: 23-Sep-2013 15:48

- Clinical laboratory tests [refer to [Section 7.4.1](#)] including chemistry, hematology, urinalysis, urinary albumin/creatinine ratio, urine pregnancy test (where applicable) [refer to [Section 7.1](#)], lipid panel, HbA1c (only if visit is at least 6 weeks after randomization), apolipoproteins (at early termination visit only), FPG, FBR plasma and serum samples ([Appendix 1](#)).

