6.5. Follow-up Phone Call

Each randomized subject should have a follow-up phone call 14 days after the last dose of investigational product to assess for AEs, SAEs and collect information on clinical events per [Section 7.8](#), if applicable. The phone call should be completed within a ± 3 day window.

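### The protocol states no route by which a Week 104 DXA scan meeting its own bone-loss thresholds reaches the investigator or the subject

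*Combined protocol and SAP*

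**What the plan says.** Section 7.6.1 (Bone Mineral Densitometry) lists three scheduled follow-up scans: "Follow up DXA scans will be performed at Week 26, 52 and 104 visits and submitted to the Central Evaluation Facility for assessment". It sets one disclosure rule for all of them: "Investigators will remain blinded to the results of these follow up scans, unless the subject meets criteria for rescue criteria as provided below".

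Section 7.6.1.1 (Rescue Criteria Related to Loss of BMD) supplies the criteria. A subject must have both a BMD fall of more than 7% from baseline at any site and a T-score below -2.5. Such subjects, "at the Week 26 or Week 52 follow-up scans, will have a complete unscheduled DXA performed". On the confirmatory scan: "The repeat, confirmatory DXA should be performed within 4 weeks from the initial reading". If the finding is confirmed, bone-active treatment is allowed while study drug continues.

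For the end of the trial, Section 6.4.4 says "Completion of the Week 104 (V15) visit marks the end of" participation in Phase B. It states when the Week 104 DXA may be done, but nothing about returning the result. Section 6.5 then provides one further contact: "Each randomized subject should have a follow-up phone call 14 days after the last dose of investigational product". Its stated purpose is "to assess for AEs, SAEs and collect information on clinical events per" Section 7.8. DXA results are not mentioned.

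**The concern.** A single rule does two jobs. It lifts the in-trial ban on bone-active drugs (Section 4.2, exclusion 31 and its note), and it is the only stated way for a follow-up scan to become known to the site. Limiting it to Weeks 26 and 52 suits the first job. For the second, it leaves the last scan without an alert.

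That scan matters for three reasons.

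- Section 3 calls the collection of BMD safety data a key purpose of the extension, and Week 104 BMD is objective 21 in Section 2.1.
- Week 104 is the scan with the longest exposure. The last scan that carries an alert is at Week 52, so 104 - 52 = 52 of the 104 treatment weeks come after it.
- Exclusion 13 removes anyone with a T-score below -2.5 at screening, so a subject below that line at Week 104 would have a measured T-score that crossed it during the trial. Section 1.5 says people in that range would probably be using drugs such as bisphosphonates. The result therefore bears on the subject's usual care just as trial participation ends.

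**Working it through.** No figure in the plan bears on this point, so the check is a reading of the text. The scheduled scans compare as follows.

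| Scan | Read centrally (7.6.1) | Stated position on the result | Rescue criteria apply (7.6.1.1) | Stated route to the site |
|---|---|---|---|---|
| Screening | Yes | Eligibility result returned before Day 1 (7.6.1) | Not applicable | Yes |
| Week 26 | Yes | Investigator blinded (7.6.1) | Yes | Yes, if both thresholds are met |
| Week 52 | Yes | Investigator blinded (7.6.1) | Yes | Yes, if both thresholds are met |
| Week 104 | Yes | Investigator blinded (7.6.1) | No | None |

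At screening the protocol plans for the result to come back. Under Section 6.2.3, a scan not done on the S3 day must be done "at least ten days before the Day 1 visit in order that the results will be available prior to Day 1". Nothing equivalent is written for Week 104.

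The other places where a route might appear were then checked.

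1. **Schedule of Activities, footnote k, and Section 6.4.4.** These cover when scans are done, including after discontinuation. They do not cover disclosure.
2. **Section 6.5 (follow-up call).** Adverse events and clinical events only.
3. **Section 4.2, note to exclusion 31.** Permits bone-active drugs during the study under the rescue criteria and points back to Section 7.6.1.1.
4. **Section 5.2 (breaking the blind).** Opens the treatment code in an emergency, not a scan result.
5. **Section 9.5 (data monitoring committee).** Recommendations go to the sponsor. No return of individual results is stated.
6. **Section 15.1 (communication of results).** Public posting of trial results, not individual findings.

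The blinding sentence in Section 7.6.1 has one exception and no end date. It could be read loosely as an exception for any follow-up scan that crosses the thresholds, but Section 7.6.1.1 names Week 26 or Week 52, so the text does not support that reading.

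Scans done at early discontinuation are not stated to be among the blinded scans, so they are not part of this point.

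**Size.** The number affected is the number of subjects who meet both thresholds at Week 104 and were not already known to the site from Week 26 or 52. It depends on the joint chance of a loss above 7% at some site and a T-score newly below -2.5. The protocol's only spread for BMD change (SD 3.3%, Section 9.1) comes from a 50-week study of another SGLT2 inhibitor and was adopted for Week 26 precision. The protocol gives no distribution of baseline T-scores, no Week 104 spread and no correlation between sites. Any count would be invented.

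**The case against.** **The answer may lie in documents not seen.** Section 7.6.1 refers to a specific scan-analysis protocol and a separate quality-control manual, and the consent form was not available. Any of these could say how a final result is returned. This stands. A reader might infer that subjects with marked bone loss will go uninformed, and the documents do not support that. They show only that this protocol states no route.

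**The Week 26/52 limit is deliberate and correct.** The rule permits bone-active drugs while study drug continues. Treatment ends at Week 104 and the ban ends with it. This also stands. A reader might infer that Week 104 was left out of the rescue rule by mistake, or that the confirmatory DXA should be extended to it. Neither follows, because there is no rescue permission left to grant. But the end of the ban does not end the reason to tell someone, and the same rule is the only exception to the blinding.

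**Silence is not a prohibition.** The blinding sentence names investigators, does not mention subjects, and does not say that results stay withheld after the study is unblinded. That is fair as far as it goes. However, the blinding is an affirmative rule that includes the Week 104 scan, and a site or facility that follows it has no stated reason to pass a result on.

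**The thresholds were chosen for rescue, not for referral.** A subject with a T-score of -3.0 and a 6% loss would still not be told. This is true, but the same holds at Weeks 26 and 52. Reusing the existing thresholds avoids a new clinical cut-off; a different one would be a clinical choice for the sponsor.

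**A safeguard is dropped.** Section 7.6.1.1 requires confirmation before action, and any one of four sites could trigger a flag. This is a real cost. It is limited by marking the result as unconfirmed and leaving confirmation to usual care.

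**Conclusion.** The point holds as a statement about the protocol's text. Sections 7.6.1 and 7.6.1.1 together blind investigators to the Week 104 DXA and limit the only exception to Weeks 26 and 52, and no other section supplies a route. Confidence is high for that statement and does not extend to any claim of harm.

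Severity is minor. The number of subjects affected is unknown and may be small, and the unseen imaging and consent documents may already close the gap. A reader might infer that the Week 104 BMD results or the trial's conclusions are compromised. They are not: the scans are still done, read centrally and available for analysis.

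The protocol already handles similar findings this way. Section 7.4.1 masks FPG and HbA1c unless alert criteria are met, and a footnote to Table 5 directs urology referral for unexplained microscopic hematuria.

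**What to change.** First check the imaging manual, scan-reading protocol and consent form. If they already state how a qualifying Week 104 result is returned, a cross-reference in Section 7.6.1 is enough.

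Otherwise, state in Sections 7.6.1 and 7.6.1.1 that:

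- the Central Evaluation Facility applies the same joint thresholds (loss above 7% from baseline at any site and T-score below -2.5) to the Week 104 scan;
- flagged results go to the investigator, marked as a single unconfirmed reading;
- the investigator informs the subject, at the follow-up call if the reading is back by then or otherwise by a separate contact, and refers to usual care for confirmation;
- the trial requires no repeat DXA, and results below the thresholds are handled as now.

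The cost is a short protocol statement and one instruction to the facility. The scans are already done and read, so no scan, scheduled visit or analysis is added. The downsides are occasional false alarms from unconfirmed readings, a few flagged BMD results seen by sites that still have ongoing subjects, and an occasional extra site contact.

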7.7. Bone Biomarkers, PTH

Blood will be collected for analysis of biochemical markers of bone turnover. The following biomarkers will be measured during the study at the times listed in the [Schedule of Activities](#).

- Carboxy-terminal cross-linking telopeptides of Type I collagen (CTX); measured as a biomarker of bone resorption.
- Procollagen type I N-terminal propeptide (P1NP); measured as a marker of bone formation.

Parathyroid hormone (PTH) will also be measured according to the times in the [Schedule of Activities](#).

The sample(s) for measurement of bone biomarkers and PTH should not be collected if the investigational product has been discontinued for >7 days prior to the collection of the sample(s).

